While there is mounting evidence of reversibility of fibrosis and even of cirrhosis [2], diagnosis of reversible liver injury is still challenging. Efforts have been made to identify patients with chronic fibrosis while the disease is still amenable to therapy with the goal of preventing progression to cirrhosis, to decrease morbidity and mortality, and to improve the quality of life.

Traditionally, the biopsy has been the gold standard to detect and grade the hepatic steatosis and fibrosis. The biopsy, however, is an invasive procedure, associated with complications and is prone to the sampling error that can mislead the clinical outcome. A technique that can detect and grade the liver damage and can evaluate the entire liver non-invasively will be highly beneficial, especially in early and potentially reversible stages of liver disease.

Recently, stiffness-weighted magnetic resonance imaging (SW-MRI) technique, magnetic resonance elastography (MRE), and a fast dual-echo 2-point Dixon (2PD) MR imaging technique, have been shown promising results in detecting and grading the hepatic fibrosis [6, 7] and hepatic steatosis [8, 9], respectively. The value of MRE and 2PD MR imaging in liver damage prior to development of fibrosis is unknown.

This study is to validate MRE technique developed at Mayo Clinic (Rochester, MN) and modified 2PD technique using the new post-processing phase correction algorithm developed at M D. Anderson Cancer Center in oncologic and non-oncologic patients.

1. Magnetic Resonance Elastography (MRE)

The changes in MR voxel complex phase are proportional to the wavefront position, which is in turn affected by the elastic properties of the tissue within the voxel. By examining the patterns of wavefront propagation using MR magnetic field gradient waveforms synchronized with the wavefront generator, tissue elastic properties can be discerned. MRE is a modified phase-contrast MR imaging sequence to image propagating shear waves in tissue [10, 11]. The stiffness of the soft tissue can be estimated from the measured wave.

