2.0 Objectives

The purpose of the study is to validate the MRE and 2PD MRI technique using the new post-processing phase correction algorithm in evaluating chronic liver disease, specifically the hepatic inflammation, steatosis, steatohepatitis, hepatic fibrosis and cirrhosis in patients with biopsy proven or clinically suspected hepatic steatosis and/or fibrosis.

Primary goals:

1. To assess the association between the degree of stiffness as measured by MRE in kPa and histopathological grades of fibrosis and steatohepatitis
2. To assess the association between the % fat fraction (FF) measured from 2PD MRI and histopathological grade of hepatosteatosis and steatohepatitis.

Secondary goal:

To evaluate the roles of MRE and 2PD MRI in predicting the steatohepatitis and hepatic inflammation.

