3.1 MRE

Overall quality of images will be evaluated based on the 1) line profile along the direction of wave propagation from each wave images, and 2) wavelength obtained by using a direct peak-to-peak measurement. The quality will be graded using a 5-point grading system: 1 being barely visible wave and 5 being the best.

The shear stiffness will be measured in kPa from the representative areas, up to 3 sites per patient.

3.2. 2PD MR images

The signal intensity (SI) will be measured on both fat (SI_f) and water (SI_w) images from the same area of region of interest. Then, % fat fraction (FF) will be calculated as $SI_f / (SI_f + SI_w)$ from FO and WO MR images.

4. Histopathological analysis

In Group I, core biopsies (at least 1.5 cm size) will be performed from up to 3 sites that are correlated with the representative areas for steatosis and fibrosis from MRE. The biopsy materials (slides) will be checked out by our collaborator at VAMC and will be hand-carried to our pathologist collaborator at MDACC for the study specific review. In group 2, surgical biopsies will be performed in the same manner.

The biopsy specimens will be evaluated and scored for hepatic steatosis, hepatic steatohepatitis, and fibrosis, based on the multiple histopathological features: 1) % of hepatocytes with macrovesicular steatosis (none, <5%, 5-33%, 33-66%, >66%), 2) location of macrovesicular steatosis (periportal, centrilobular, azonal, panacinar), 3) microvesicular steatosis (absent, present), 4) lobular neutrophilic and lymphocytic inflammation (per 200x field), 5) ballooning degeneration (score 0-1 = none, few, many), 6) acidophilic bodies (absent, present), and 7) Mallory's hyaline (absent, present), and 8) fibrosis (none, perisinusoidal, mild and moderate portal, mild and moderate periportal, bridging, cirrhosis) [23].

4.1. Hepatic steatosis will be graded using 4 point grading system; 0 being no steatosis, 1 being <30%, 2 being ≥ 30 - <60%, and 3 being $\geq 60\%$.

4.2. Hepatic steatohepatitis will be scored using 9 point grading system based on the sum of steatosis score (0 being <5%, 1 being 5-33%, 2 being >33-66%, 3 being >66%), lobular inflammation (score 1-3), and ballooning (score 0-2) [22].

4.3. Hepatic fibrosis will be graded using 5 point grading system, 0 being none, 1 being sinusoidal, 2 being mild to moderate portal, 3 being mild to moderate periportal, 4 being septal).

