5.0 Statistical Analysis

1. Design

This is a pilot study designed to evaluate MRE and 2PD as alternatives to liver biopsy in evaluating fibrosis, steatohepatitis, and hepatosteatosis in patients with liver disease. There are two groups of patients in the study: patients in Group 1 will have advanced liver disease, while Group 2 will be for patients who undergo hepatectomy or core biopsy. We expect to enroll 30 patients into each group for a total of 60 patients. The number of accrual in Group 2 will be recalculated as needed upon completion of data analysis for the first 30 patients.

2. Analyses

For the first primary objective, the association between degrees of stiffness measured by MRE in kPa and histopathological grades of fibrosis and steatohepatitis will be assessed using Pearson correlation.

For the second primary objective, the association between % fat fraction measured by 2PD MR images and histopathological grade of hepatosteatosis and steatohepatitis will be assessed using Pearson correlation.

Because the above analyses assume that the fibrosis, steatohepatitis and steatosis grades are continuous variables, analyses will be repeated using rank correlation methods. In addition, as a secondary statistical analysis, we will perform ordinal regression analyses to evaluate the individual ability of MRE kPa and 2PD MRI %FF measurements and combination of both as covariates to predict grades of fibrosis, hepatosteatosis, and steatohepatitis for these patient populations.

3. Sample Size and Power

With 30 patients in each group, for each of the four correlations above, there will be 90% power to detect a correlation of at least 55% between the kPa or the %FF and the histopathological grade, assuming a two-sided alpha=0.05 level test for a non-zero correlation.

Although there are four separate primary comparisons being performed simultaneously, no correction will be made for the multiplicity of testing due to the pilot nature of the study. Each of the two primary objectives (two comparisons each) will have a Type I error rate (alpha level) of no more than 10%.1. Degree of stiffness measured from MRE in kPa will be correlated with histopathological grades of fibrosis and steatohepatitis.

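### The secondary goal names hepatic inflammation as a prediction target, but no planned analysis has inflammation as its outcome

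*Combined protocol and SAP*

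**What the plan says.** 2.0 Objectives gives the secondary goal as: "To evaluate the roles of MRE and 2PD MRI in predicting the steatohepatitis and hepatic inflammation". The purpose statement in the same section also lists inflammation as a condition of its own: "specifically the hepatic inflammation, steatosis, steatohepatitis, hepatic fibrosis and cirrhosis".

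5.0 Statistical Analysis, 2. Analyses, plans four Pearson correlations: kPa with fibrosis and with steatohepatitis, and %FF with hepatosteatosis and with steatohepatitis. These are repeated with rank methods. Ordinal regressions on kPa, on %FF and on both are then used "to predict grades of fibrosis, hepatosteatosis, and steatohepatitis for these patient populations".

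In 4.0 Study Plan, 4. Histopathological analysis, the recorded features include "lobular neutrophilic and lymphocytic inflammation (per 200x field". Item 4.2 reads "Hepatic steatohepatitis will be scored using 9 point grading system based on the sum of steatosis score", with steatosis running 0 to 3, plus "lobular inflammation (score 1-3), and ballooning (score 0-2". The feature list above it gives a different ballooning range: "ballooning degeneration (score 0-1 = none, few, many".

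**The concern.** The secondary goal names two targets and the analysis section covers one. Followed exactly, the plan would report nothing on how either technique relates to inflammation, although the pathologist will have scored it. The steatohepatitis result cannot stand in for it, because that score sums inflammation with steatosis and ballooning, and the goal lists the two targets separately.

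A related limit affects one of the four primary correlations. %FF measures fat, and the steatohepatitis score contains a fat component. A significant correlation between them would not tell the reader whether 2PD MRI tracks anything besides fat, and no planned analysis separates the two.

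**Working it through.** **1. Outcomes planned, set against the goal.**

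| Analysis in 5.0 | Outcomes |
|---|---|
| Pearson, kPa | fibrosis, steatohepatitis |
| Pearson, %FF | hepatosteatosis, steatohepatitis |
| Rank repeats | the same |
| Ordinal regression | fibrosis, hepatosteatosis, steatohepatitis |

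Inflammation is in no row. The model with both kPa and %FF does not supply it, because histological steatosis stays inside the outcome.

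**2. Score ranges in 4.2.** Steatosis 0–3, inflammation 1–3 and ballooning 0–2 give totals from 0+1+0 = 1 to 3+3+2 = 8. That is eight values against a stated 9 points. Nine values (0–8) would need inflammation 0–3. With inflammation 1–3 and ballooning 0–1, as in the feature list, there are seven (1–7). A range of 1–3 also leaves no level for absent inflammation.

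**3. The plan's own power figure.** n = 30, r = 0.55, two-sided alpha 0.05, Fisher z: atanh(0.55) × √27 = 0.618 × 5.196 = 3.213; 3.213 − 1.96 = 1.253; Φ(1.253) = 0.895. The stated 90% is reproduced, and the same formula is used below.

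**4. How far fat alone can drive the %FF–steatohepatitis correlation (illustration).** The documents give no score distributions and no correlation of %FF with steatosis. Assumptions: component levels evenly spread; %FF carries only fat; steatosis independent of the other two components; r(%FF, steatosis) from 0.55 to 0.9; inflammation–ballooning correlation c from 0 to 0.5.

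- Variances: 0–3 scale, 1.25; 1–3 or 0–2 scale, 0.667.
- Induced r = r(%FF, steatosis) × √(1.25 / Var(total)).
- Upper end (4.2 ranges as written, c = 0): Var(total) = 1.25 + 0.667 + 0.667 = 2.583; share 1.25/2.583 = 0.484; r = 0.9 × √0.484 = 0.626; significant in 97% of studies.
- Lower end (inflammation 0–3, c = 0.5): Var(total) = 1.25 + 1.25 + 0.667 + 2 × 0.5 × √(1.25 × 0.667) = 4.079; share 0.306; r = 0.55 × √0.306 = 0.304; significant in 37%. At c = 0.3 the figure is 40%, and at c = 0 it is 47%.
- Middle case (4.2 ranges as written, c = 0, r(%FF, steatosis) = 0.8): r = 0.8 × 0.696 = 0.556, about the design value of 0.55, with no link to inflammation or ballooning.

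**5. Why an unadjusted check is not enough.** If steatosis correlates 0.3, 0.4 or 0.5 with the inflammation + ballooning subscore and r(%FF, steatosis) = 0.8, fat alone induces r = 0.24, 0.32 or 0.40 between %FF and that subscore. It is then significant in about 25%, 41% or 60% of studies. In simulations at n = 30 with fat driving all components, the unadjusted subscore test was significant in 21–97% of trials. The partial test given the four-level steatosis score was significant in about 5–17%, depending on the model.

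**6. Precision at n = 30.** The 95% half-width around zero is tanh(1.96/√27) = 0.36 (partial: tanh(1.96/√26) = 0.37). For 80% power, atanh(r) = (1.96 + 0.842)/√27 = 0.539, so r = 0.49 (partial: 0.50).

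**The case against.** This is a pilot, and neither primary goal mentions inflammation. The Design paragraph of 5.0 names only fibrosis, steatohepatitis and hepatosteatosis, and the steatohepatitis score does contain lobular inflammation. So the gap is half of one secondary goal. That description is fair and sets the weight of the point, but it does not close the gap, because the goal lists inflammation apart from the score that absorbs it.

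Several stronger readings are tempting and are not supported.

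- A reader might infer that the primary %FF–steatohepatitis correlation is circular or invalid. It is not. The goal promises an association with the grade, the test of a non-zero association is sound, and no passage claims detection beyond fat. The hepatosteatosis correlation is also reported beside it. It does not isolate the remainder of the score, but the overlap limits interpretation only.
- A reader might take the Background sentence, "The value of MRE and 2PD MR imaging in liver damage prior to development of fibrosis is unknown", as a commitment to study inflammation. Damage before fibrosis also covers steatosis and steatohepatitis, which are analysed. List order in the purpose statement does not establish priority.
- A reader might infer that inflammation cannot be analysed until the whole score is settled. Only the inflammation range is needed for that. The ballooning range and the 9-point total matter for the steatohepatitis score and the exploratory subscore. The 0–1 range carries three labels, so it may be a slip.

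**Conclusion.** The mismatch between objective and analysis holds on the text alone and rests on no assumption: one of the two targets in the secondary goal has no analysis, although the data will be collected. It should be corrected. It invalidates no primary analysis and leaves the 90% power statement unchanged.

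The scoring inconsistency also holds by counting: eight possible totals against nine stated, and two ranges for ballooning.

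The fat overlap supports only an optional exploratory analysis. Its size, an induced r of about 0.30–0.63 and significance in about 37–97% of studies at n = 30, is an illustration under the assumptions in step 4 of the working. It is not a prediction for this trial.

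**What to change.** In 5.0, 2. Analyses:

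- Add the lobular inflammation score as a further outcome of the planned ordinal regressions (kPa, %FF, both). State that lobular inflammation is the measure of hepatic inflammation, which the documents do not define. Report confidence intervals, and label the result secondary and unadjusted for multiplicity.
- Optional and exploratory: report the partial rank correlation of %FF with the inflammation + ballooning subscore, given the 4.2 steatosis score (the 4.1 grade has different cut-points). State that unadjusted results support no claim of detection beyond fat.

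In 4.0, 4. Histopathological analysis, before any scoring: reconcile the inflammation range 1–3 with the 9-point total, and the two ballooning ranges with each other.

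Cost: no new data. Three more ordinal models per analysis set (six if run by group), plus one exploratory partial correlation per set. Counting one test per marker coefficient gives 1 + 1 + 2 + 1 = 5 per set, so the chance of at least one false positive is at most 5 × 0.05 = 25%, or 10 × 0.05 = 50% by group. Intervals will be wide (about ±0.36 on the correlation scale at n = 30), and sparse inflammation levels may make the ordinal models unstable. The partial test keeps some residual fat. It is also weak when %FF tracks steatosis closely: variance inflation 1/(1 − r²) is 1.4 at r = 0.55 and 5.3 at r = 0.9.

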3.0 Patient Eligibility

The study will have 2 groups of patients with a total of 30 patients each.

A total of 30 patients (Group 1) with biopsy proven or clinically suspected advanced parenchymal liver disease (fatty liver, fibrosis, and cirrhosis) will be recruited from VA Medical Center in Houston. An additional 30 patients (Group 2) will be recruited among those who are registered at MDACC and who are suspected to have hepatic damage, hepatic steatosis, hepatitis, hepatic fibrosis or cirrhosis clinically or radiographically. The number of accrual in Group 2 will be adjusted as needed upon completion of data analysis for the first 30 patients.

The patients recruited at MDACC will be approached by either the Diagnostic Imaging faculty or Research Staff, including research nurses and research coordinators for their consent prior to their procedure. During the consenting process patients will be educated and consented for their research participation in this study.

Inclusion criteria:

Group 1

1. Biopsy proven or clinically suspected advanced parenchymal liver disease
2. Core biopsies performed within 1-month* of MRI/MRE
 3. No treatment affecting the status of liver between MRI/MRE and post-imaging biopsy
4. Signed consent

*The interval between the biopsy and MRI/MRE is allowed for up to 8 weeks if the liver condition is thought to be stable during this time per a collaborating hepatologist.

Group 2

1. Clinically or radiographically suspected liver damage, hepatic steatosis, hepatitis, hepatic fibrosis or cirrhosis
2. Surgical or core biopsy scheduled within 4 weeks* of MRI/MRE
3. Signed consent

*The interval between the biopsy and MRI/MRE is allowed for up to 8 weeks if the liver condition is thought to be stable during this time per the primary physician.

Exclusion criteria:

1. Claustrophobia
2. Contraindications for MRI
3. Unable to hold a breath
4. Ascites or other clinical or radiographical signs of portal hypertension

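### Does the 10% Type I error per objective fail to hold because the power calculation implies tests in two groups?

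*Combined protocol and SAP*

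**What the plan says.** Section 2.0 states each primary goal once, without naming a group; the first is "To assess the association between the degree of stiffness as measured by MRE in kPa and histopathological grades of fibrosis and steatohepatitis". The Analyses part of section 5.0 assigns Pearson correlation to both goals and does not say whether the groups are analysed separately or pooled.

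The Design part of section 5.0 gives the size: "We expect to enroll 30 patients into each group for a total of 60 patients". The Sample Size and Power part continues: "With 30 patients in each group, for each of the four correlations above, there will be 90% power" for a correlation of at least 0.55, with a two-sided 0.05 test of zero correlation.

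The next paragraph deals with multiplicity: "Although there are four separate primary comparisons being performed simultaneously, no correction will be made for the multiplicity of testing", and gives the pilot nature of the study as the reason. It then states the error rate: "Each of the two primary objectives (two comparisons each) will have a Type I error rate (alpha level) of no more than 10" per cent.

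Section 5.0 also allows the second group to be resized: "The number of accrual in Group 2 will be recalculated as needed upon completion of data analysis for the first 30 patients". Section 3.0 says much the same.

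**The concern.** The power sentence and the error sentence seem to count tests differently. Power is given for 30 patients in each group, which suggests that each of the four correlations is tested once in Group 1 and once in Group 2, eight tests in all. The error sentence counts two tests per objective and names no group, while section 2.0 sets each objective for the study as a whole. Read together, an objective would carry four tests at 0.05, and the printed cap would cover only half of them.

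The accuracy of a stated error rate would then be at stake. A reader could believe that the chance of at least one false-positive association per objective is capped at 10% for the study, when over both groups it could be higher. There is also an analytic ambiguity: one analyst might run two sets of 30 and another a single set of 60.

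**Working it through.** **Inputs, all from section 5.0:** 30 patients per group, 60 in total; correlation 0.55; two-sided alpha 0.05 per test; four comparisons, two per objective; no multiplicity correction.

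**1. Reproduce the power.** By the Fisher z approximation, power ≈ Φ(atanh(r)·√(n−3) − 1.960), with atanh(0.55) = 0.6184.

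- n = 30: 0.6184 × √27 = 0.6184 × 5.196 = 3.213; 3.213 − 1.960 = 1.253; Φ = 0.895. A simulated t-test of the Pearson correlation gives 0.904. The stated 90% reproduces.
- n = 60: 0.6184 × √57 = 0.6184 × 7.550 = 4.669; 4.669 − 1.960 = 2.709; Φ = 0.997. The stated 90% does not reproduce.

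The detectable correlation at 90% power is tanh((1.960 + 1.282)/√(n−3)): 0.554 at n = 30 and 0.405 at n = 60. The printed pair of 90% and 0.55 therefore belongs to a test on 30 patients.

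**2. Reproduce the error rate.** For two tests at 0.05 the bound is 2 × 0.05 = 10%; if independent, 1 − 0.95² = 9.75%. The stated cap is right for the two tests it counts.

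**3. Compare the two readings.**

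| Reading | Tests per objective | Power at 0.55 | Printed 90% | Printed 10% cap |
|---|---|---|---|---|
| Each group on its own, n = 30 | 2 in that group | 89.5% | matches | holds in that group |
| Groups pooled, n fixed at 60 | 2 | 99.7% | conservative | holds |

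The first reading satisfies every figure in the paragraph. The second leaves the cap correct and only understates power.

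**4. Where the larger figure comes from.** Take both groups as one family, so that an objective has 2 × 2 = 4 tests. The bound is 4 × 0.05 = 20%; if independent, 1 − 0.95⁴ = 18.5%. The two tests within a group share the same imaging measurement, and section 4.0 (item 4.2) builds the steatohepatitis score partly from a steatosis score, so positive correlation is likely. The documents give no value for it. With assumed correlations between the two test statistics in a group, bivariate normal, and independent groups, the two-group rate is 1 − (1 − one-group rate)²:

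| Assumed correlation | One group | Both groups as one family |
|---|---|---|
| 0 | 9.75% | 18.5% |
| 0.5 | 9.07% | 17.3% |
| 0.7 | 8.35% | 16.0% |
| 0.9 | 7.04% | 13.6% |
| 1 (limit) | 5.00% | 9.75% |

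The last column depends on a choice of family that the plan does not make. No sentence says that a positive result in either group counts as success for an objective. Section 5.0 describes the groups as different populations: advanced liver disease in one, patients having hepatectomy or core biopsy in the other.

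**The case for a change.** The strongest case for a change is that the sponsor chose to print a cap, and a printed cap should have a clear scope. The sentence refers to the two primary objectives and not to a group, and section 2.0 sets those objectives for the whole study. If the groups are tested separately and counted together, the rate exceeds 10% at every within-group correlation short of near-perfect. Declining a correction does not make a stated rate accurate. By-group testing is itself only inferred from the power figure, so a pooled analysis could be chosen later with some support from the text.

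Part of this stands. The plan does not say in words whether the primary correlations are by group or pooled, and the error sentence names no group. Those are real omissions, and the 20% arithmetic is correct for the family it assumes.

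The inference from omission to error does not stand. The paragraph on power and error opens with 30 patients in each group, and the error sentence shows its basis by counting two comparisons. A statistician following section 5.0 would run the correlations in each group and read the 10% accordingly. The wish to analyse the first 30 patients before settling Group 2 accrual fits that reading too. How that accrual is settled is a separate question.

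**Conclusion.** The concern does not call for a change. Both printed figures are right for one group of 30: power 89.5% against the stated 90%, and a two-test bound of exactly 10%. The bound of 20% per objective (18.5% if all tests are independent, 13.6% at an assumed within-group correlation of 0.9) needs both groups to be counted as one family, which the documents do not do.

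What remains is a scope left implicit, which analysts can fill from the power sentence. Writing it down would alter no patient, measurement, test or decision rule. Nothing in the plan turns on the 10%, and the plan is open that its comparisons are uncorrected because the study is a pilot. A reader who prefers to count both groups together can do so from the reported correlations.

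This rests on two assumptions: that by-group analysis is intended, as the power figure indicates but no sentence states, and that the groups are independent samples. If the sponsor instead pooled a fixed 60 patients, the 10% would still hold and the 90% would be conservative, with 90% power already reached at a correlation of about 0.40.
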